13.2. Definition of Baseline

Unless stated otherwise, baseline will be defined as the last available pre-treatment value taken on or before the first dose date of study drug, and will be used for summary of baseline characteristics, as well as for all change-from-baseline analyses of efficacy and safety endpoints.

13.3. Definition of Relative Study Days

Unless otherwise noted, relative study days (Rel Days) of an evaluation are defined as number of days relative to the first dose date of study drug which is designated as Day 1, and the preceding day is Day -1, the day before that is Day -2, etc.

If evaluation date is on or after first dose date, then relative study days are calculated as

$$\text{Evaluation date} - \text{first dose date of study drug} + 1.$$

If evaluation date is before first dose date, then relative study days are calculated as

$$\text{Evaluation date} - \text{first dose date of study drug}$$

Relative study days take negative values if evaluation date occurs prior to first dose date and take positive values if evaluation date occurs on or after first dose date of study drug.

13.4. Definition of Visit Windows

All assessments occurring on or before the first date of dosing (Analysis Study Day (ADY) ≤ 1) will be assigned to the Baseline analysis visit window.

Unless otherwise specified, the actual scheduled nominal post-baseline visit will be used for over time summaries. Post-baseline unscheduled visits and early termination visits will be mapped to a scheduled visit and will only be used in the analysis if the nominal scheduled visit result is missing, [Table 5](#) and [Table 6](#) presents the analysis visit window mapping for unscheduled and early term visits. In the case that multiple unscheduled or early termination visits are in the same analysis window, the one closest to the target date will be used. In the event that windowed visit is mapped to an illogical sequence of visits when considering nearby scheduled visits

(i.e., windowed visit is higher than the subsequent visit or lower than the preceding visit), the windowed visit will be set to the logical scheduled visit.

Table 5: Post-Baseline Analysis Visit Window for Unscheduled and Early Termination Visits: Monthly Regimen

Analysis Visit	Target Study Day	Analysis Window (days)
Day 7	7	2 to 15
Month 1	30	16 to 45
Month 2	60	46 to 75
Month 3	90	76 to 105
Month 4	120	106 to 135
Month 5	150	136 to 165
Month 6	180	166 to 195
Month 7	210	196 to 225
Month 8	240	226 to 255
Month 9	270	256 to 285
Month 10	300	286 to 315
Month 11	330	316 to 345
Month 12	360	346 to 375
Month 13	390	376 to 405
Month 14	420	406 to 435
Month 15	450	436 to 465
Month 16	480	466 to 495
Month 17	510	496 to 525
Month 18	540	526 to 555
Month 19	570	556 to 585
Month 20	600	586 to 615
Month 21	630	616 to 645
Month 22	660	646 to 675
Month 23	690	676 to 705
Month 24	720	706 to EOS

Table 6: Post-Baseline Analysis Visit Window for Unscheduled and Early Termination Visits: Every Other Month Regimen

Analysis Visit	Target Study Day	Analysis Window (days)
Day 7	7	2 to 15
Month 1	30	16 to 45
Month 2	60	46 to 75
Month 3	90	76 to 105
Month 4	120	106 to 135
Month 5	150	136 to 165
Month 6	180	166 to 195
Month 7	210	196 to 225
Month 8	240	226 to 255
Month 9	270	256 to 285
Month 10	300	286 to 315
Month 11	330	316 to 345
Month 12	360	346 to 375
Month 14	420	376 to 450
Month 16	480	451 to 510
Month 18	540	511 to 570
Month 20	600	571 to 630
Month 22	660	631 to 690
Month 24	720	690 to EOS

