**APPENDIX B: VISIT SCHEDULE—Monthly Group—Month 13 to Month 24**

	Treatment												Early Term A
Visit #	15	16	17	18	19	20	21	22	23	24	25	26	
Day	390	420	450	480	510	540	570	600	630	660	690	720	
Week	52	56	60	64	68	72	76	80	84	88	92	96	
Month	13	14	15	16	17	18	19	20	21	22	23	24	
Window (+ or - days)	8	8	8	8	8	8	8	8	8	8	8	8	
Informed Consent/Assign Screening Number													
Demographic Data													
Inclusion/Exclusion Criteria B													
Medical/Surgical/Ocular History C													
Blood Draw—Safety Labs D,E,F						x						x	x
Urine Sample Collection D,E,F						x						x	x
Urine Pregnancy Test D,E,F	x	x	x	x	x	x	x	x	x	x	x	x	
Blood Draw—PK and Complement Profile (C3, CH50, AH50) D,S												x	x
Blood Draw—Genotyping (if applicable) D													
Blood Draw—Anti-Pegcetacoplan Ab D		x				x						x	x
Blood Draw for Clinical Repository (if applicable) D,G												x	x
Vital Signs H	x	x	x	x	x	x	x	x	x	x	x	x	x
Physical Examination I												x	x
BCVA J	x	x	x	x	x	x	x	x	x	x	x	x	x
LL-BCVA I	x	x	x	x	x	x	x	x	x	x	x	x	x
MNREAD or Radner Reading Charts (select countries) J,K						x						x	x
Slitlamp Examination	x	x	x	x	x	x	x	x	x	x	x	x	x
Endothelial Cell Count S												X	X
NEI VFQ-25 L						x						x	x
FRI L						x						x	x
Dilated Indirect Ophthalmoscopy	x	x	x	x	x	x	x	x	x	x	x	x	x
Home-Based Digital Applications L,M,S						x						x	

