A. For subjects that discontinue the study early, the early termination assessments should be performed after a minimum of 30 days have passed from the last dosing visit. If a subject reports for a scheduled visit and decides to terminate early prior to dosing, the visit should be considered the early termination visit and all early termination procedures should be performed. At Month 24, all subjects should be offered entry into an open-label study.

B. At Day 1 (Visit 2), confirm subject eligibility through reviewing the inclusion/exclusion criteria and receive confirmation of eligibility from the reading center.

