1. INTRODUCTION

This study is being conducted as part of a series of studies for the clinical development of pegcetacoplan (also known as APL-2) for geographic atrophy [GA] secondary to age-related macular degeneration (AMD). This statistical analysis plan (SAP) provides a technical and detailed elaboration of the statistical analyses of efficacy, safety, and pharmacokinetic data, supplementing what is described in the final study protocol, version 1.0, amendment 5, dated 12 August 2020.

The primary study analysis will be based on complete data from the first 12 months of the study and performed after all subjects have completed the Month 12 visit in the study or discontinued early, and all corresponding data have been entered into the database, reviewed, cleaned, and finalized as the Month 12 dataset. Analysis will include testing of hypotheses of the primary efficacy endpoint at Month 12. Key secondary, secondary, and exploratory endpoints will be evaluated based on data in the Month 12 datasets in a descriptive manner. An analysis of the safety data in the Month 12 dataset will also be performed.

The final study analysis will be based on data after all subjects have either completed the Month 24 visit in the study or discontinued the study early, and all data from the study are in the database and the database is reviewed, cleaned, and locked as the final dataset. Analysis will include testing of hypotheses of the key secondary endpoints at Month 24 as described in Section 6.3.1. A cumulative analysis of all data through the end of the study will be produced based on the final dataset.

See Section 3.5 for further details on analysis timing.

The analyses specified in this document supersede the analysis plan described in the study protocol (protocol version 1.0, amendment 5 dated 12 August 2020).

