4. STATISTICAL ANALYSIS SETS

Two sham treatment arms (SM and SEOM) will be pooled into a single control (Sham) group for analyses.

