6.2.6. Full 24 Month Analyses

In general, the same analysis approach for the changes from baseline GA lesion size for the final reporting of the full 24 months will be repeated as described in Sections 6.2.2, 6.2.3, 6.2.4, 6.2.5. Key differences include:

- The definition of excessive missed/not received injection in the supplementary estimand will be defined based on the Month 24 period. The threshold for missed/not received injections due to the COVID-19 pandemic is missing 4 or more injections for the Monthly schedule group and 2 or more injections for the EOM schedule group prior to the Month 24 visit attributable due to the COVID-19 pandemic.
- The Month 12 PP set will be replaced with the Month 24 PP set for the supplementary analysis.

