6.3.2.3. NL-BCVA Score

The mean NL-BCVA score for the study eye will be summarized and analyzed in a similar fashion as the primary efficacy endpoint using MMRM described in Section 6.2.2. The model will include treatment (PM, PEOM, Sham), presence of CNV in the fellow eye (yes or no), and baseline GA lesion area ($< 7.5 \text{ mm}^2$ or $\geq 7.5 \text{ mm}^2$) as fixed effects; baseline NL-BCVA score as a covariate, time (in months) as a factor; the time \times treatment interaction term as well as the baseline NL-BCVA score \times time interaction term. Note, for the second year, only timepoints that were measured for all three treatment groups will be included in the model.

The observed values for the NL-BCVA will be summarized by treatment group and visit for both the study and the fellow eye. Summaries will present the descriptive statistics for baseline, absolute values and change from baseline data.

The mean change from baseline in the NL-BCVA score for the study eye \pm the standard error as well as the LS mean of the change from baseline in the NL-BCVA score for the study eye \pm the standard error will be plotted over time by treatment group.

In addition, the categorical changes (improvements of ≥ 15 , ≥ 10 to < 15 , ≥ 5 to < 10 , and minimal/no change (-4 to 4), worsening of ≥ 5 to < 10 , and ≥ 10 to < 15 and ≥ 15) for the study eye will be summarized by treatment group and visit.

The shift from baseline in the NL-BCVA of the study eye categories (≥ 70 , $\geq 60 - < 70$, $\geq 35 - < 60$, $\geq 20 - < 35$, < 20 ETDRS letters over time will be presented by treatment group and visit. The above-mentioned ETDRS letter thresholds are based on WHO definitions for vision impairment and blindness. WHO criteria were implemented in an attempt to capture the progressive nature of

Geographic Atrophy and the ultimate treatment goal of avoiding successive vision impairment and blindness through application of active treatment (Pegcetacoplan vs. Sham).^[1]

The average NL-BCVA score over the last 3 months for each reporting period (Month 10 - Month 12 for the Month 12 reporting; Month 22 - Month 24 for the Month 24 reporting) will be calculated for each subject who has at least one NL-BCVA assessment in these windows. The observed values for the NL-BCVA and changes from baseline will be summarized by treatment group for the study eye. Summaries will present the descriptive statistics for baseline, absolute values and change from baseline data.

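### SAP 13.4 puts Day 690 in two windows of Table 6 and, after Month 12, maps unscheduled and early-termination values by regimen for assessments that share one schedule (minor)

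*SAP*

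**What the plan says.** SAP 13.4 keeps nominal scheduled visits as they are. For the rest, "Post-baseline unscheduled visits and early termination visits will be mapped to a scheduled visit and will only be used in the analysis" when the nominal result is missing. Table 5 (monthly) has a 30-day window for every month from 13 to 23, with Month 24 from Day 706. Table 6 (EOM) has even months only: 14 (376–450), 16 (451–510), 18 (511–570), 20 (571–630), 22 (631–690) and 24 (690 to EOS). The tables are identical through Month 12.

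The Year 2 schedules in SAP Tables 9 and 11 place FAF at Months 14, 16, …, 24 and at early termination in both regimens. The reading charts, FRI and NEI VFQ-25 are at Months 18 and 24 and at early termination in both (also Protocol Appendices B and D).

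Footnote A gives two routes to an early-termination visit: "the early termination assessments should be performed after a minimum of 30 days have passed from the last dosing visit", or, for a subject who attends a scheduled visit and "decides to terminate early prior to dosing, the visit should be considered the early termination visit".

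On analysis, SAP 4 states: "Two sham treatment arms (SM and SEOM) will be pooled into a single control (Sham) group for analyses". For GA area, SAP 6.2.6 states that "the same analysis approach for the changes from baseline GA lesion size for the final reporting of the full 24 months will be repeated". For NL-BCVA, SAP 6.3.2.3 adds: "Note, for the second year, only timepoints that were measured for all three treatment groups will be included in the model". SAP 6.4.1 has the same rule for LL-BCVA. No such sentence is given for GA area, reading speed, FRI or NEI VFQ-25.

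**The concern.** Windows by regimen make sense for assessments that follow the regimen's visits. The four assessments named above do not: in Year 2 they are planned at the same months in all arms. Table 5 nevertheless sends their early-termination values to odd months, where none is planned, on days that Table 6 assigns to a neighbouring even month. A value from Day 700 is Month 23 in PM and SM but can supply Month 24 in PEOM and SEOM. Because SM and SEOM are pooled, the control group is built under both rules.

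Day 690 is a separate error of wording. It can be reached in practice, and the choice decides whether the value is redundant (Month 22 already observed) or supplies Month 24. At stake is a pre-specified inclusion rule that does not depend on randomized regimen or on a programmer's choice.

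**Working it through.** **Inputs.** Window limits from SAP Tables 5 and 6; schedules from SAP Tables 9 and 11; growth rates 1.47, 1.70 and 2.13 mm²/year and SD 1.5 mm² from SAP 3.4. The plan states no figure to reproduce on this point.

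**Spacing of the tables (inferred, not stated).** Target −14/+15 days reproduces every Table 5 window through Month 23, and 720 − 14 = 706 is the printed start of Month 24. Target −29/+30 days reproduces Table 6 Months 16 to 22 and the upper limit of Month 14. The same rule gives 720 − 29 = 691 for Month 24; the table prints 690.

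**Day-by-day comparison, Days 376–705 (705 − 376 + 1 = 330 days).**

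| Days | Table 5 | Table 6 | Days differing |
|---|---|---|---|
| 376–405 | 13 | 14 | 30 |
| 436–465 | 15 | 14 to Day 450, then 16 | 30 |
| 496–525 | 17 | 16 to Day 510, then 18 | 30 |
| 556–585 | 19 | 18 to Day 570, then 20 | 30 |
| 616–645 | 21 | 20 to Day 630, then 22 | 30 |
| 676–705 | 23 | 22 to Day 689, both on Day 690, then 24 | 30 |

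Total 6 × 30 = 180 of 330 (54.5%), all in Table 5 odd-month windows. Days 16–375 and Day 706 onward: none. For the assessments planned only at Months 18 and 24, the days that matter are 511–525 and 556–570 (Month 18 only under Table 6) and 691–705 (Month 24 only under Table 6): 3 × 15 = 45 days, plus the ambiguous Day 690.

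**Day 690.** The Month 22 target is Day 660, and 660 + 30 = 690. The SAP tie rule covers several visits in one window. Protocol 12.11 covers two visits equidistant from a target. Neither covers one visit in two windows. The sequence rule in 13.4 does not help either, since after a Month 22 visit both labels are in order.

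**Share of Year 2 early-termination FAF images that reach an even month with no scheduled image (monthly / EOM).** Assumed: last doses on target and spread evenly over Months 12–23 (monthly) or 12–22 (EOM), images before Day 712, Day 690 read as Month 22.

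| Route | SAP windows | Corrected Table 6 in both regimens |
|---|---|---|
| 30–44 days after last dose | 45% / 94% | 97% / 94% |
| 30–60 days after last dose | 48% / 97% | 98% / 97% |
| Before dosing, visits on target | 45% / 100% | 55% / 100% |

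On the last route the monthly figures are 5/11 and 6/11 visits. The 55% depends on exact timing. With visits spread evenly over ±8 days there are 11 × 17 = 187 visit-days. Of these, 85 (even months) + 17 (Month 13) + 5 × 8 (the days after target at Months 15, 17, 19, 21 and 23) = 142 are used, or 76%.

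**Effect on Month 24 GA area.** Estimated with generalized least squares means at Months 2–24, n = 200/200/100+100, linear growth and random slopes. Assumed: measurement SD 0.15–0.5 mm², Year 2 dropout 5–15% in all arms or 15% active and 5% sham, and an early-termination image for every dropout. Largest absolute bias:

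- PM: 0.0054 mm² under the SAP, 0.0043 with common windows.
- PEOM: 0.0068 and 0.0059.

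The improvement is about 0.001 mm². The differences implied by linear growth are 2 × (2.13 − 1.47) = 1.32 mm² (PM) and 2 × (2.13 − 1.70) = 0.86 mm² (PEOM). The standard error changes by at most 0.05%.

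**The case against.** The best case for leaving the tables alone is that the SAP maps to a scheduled visit, and the EOM arms have no odd-month visit in Year 2. That explains two tables for visit-based data such as NL-BCVA. It does not explain them for assessments with a common schedule.

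Three objections stand and limit the point. First, 180 of 330 counts calendar days. A reader might infer that more than half of Year 2 images or patients are handled differently. The documents do not support that, because the mapping acts only on unscheduled and early-termination visits with a missing nominal result, and subjects who stop treatment can stay on nominal visits. Second, part of the gap comes from the visit schedule: monthly subjects can leave at odd-month visits, and common windows still leave 55% / 100% (76% / 100% with visits spread over the window) on the pre-dose route. Third, common windows have boundaries of their own. Days 450, 510, 570, 630 and 690 are odd-month targets in the monthly arms, so one day decides whether an image is used.

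A reader might also infer that the tested Month 24 endpoints are biased. The SAP does say "Analysis will include testing of hypotheses of the key secondary endpoints at Month 24 as described in Section 6.3.1", but no effect was computed for them. The Month 24 exposure is Days 691–705 (and Day 690 in the EOM arms). In the monthly arms it excludes anyone dosed at Month 23 who then waits 30 days: 690 − 8 + 30 = Day 712 or later, which is Month 24 in both tables. Under SAP 6.3.1 that testing is conditional on the primary hypotheses and is planned on pooled APL2-303/304 data, unless APL2-304 cannot pass alpha.

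**Conclusion.** The point holds as a minor one. The Day 690 overlap is wrong as written, and nothing in either document resolves it. Mapping FAF, reading charts, FRI and NEI VFQ-25 by regimen in Year 2 is an avoidable inconsistency that also splits the pooled sham group.

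It does not reach the Month 12 primary comparison, whose windows are the same in both tables. Month 24 GA area was removed from formal testing (SAP 15), and its estimated bias is below 0.01 mm² with or without common windows. That estimate rests on the assumed dropout, timing and measurement error and does not carry over to the functional endpoints. It also treats odd-month GA values as unused, which is an inference: the tipping-point example in 6.2.3.1 uses Months 2, 4, …, 12, but the SAP does not list the model's time points. For NL-BCVA the exclusion of Month 23 is explicit.

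**What to change.** 1. Start the Table 6 Month 24 window at Day 691.
2. For unscheduled and early-termination values of FAF, reading charts, FRI and NEI VFQ-25, use one set of Year 2 windows in both regimens, for example the corrected Table 6 windows, mapped only to months where that assessment is planned.
3. Leave the NL-BCVA and LL-BCVA windows as they are. Month 23 is a scheduled assessment in the monthly arms, so a Month 24 window from Day 691 would overlap Table 5 Month 23 (676–705). If a common Month 24 window is wanted for the model, define it separately and without overlap.
4. Report the number and timing of substituted values by arm.

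The Year 1 windows, the primary analysis and the SAP 3.6 cutoff stay unchanged.

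The cost is SAP wording and derivation code. The statistical downside is that a monthly-arm substitute may be up to 30 days off target, or 44 at the start of Month 14 (420 − 376), instead of 15. At sham growth of 2.13 mm²/year that is 2.13 × 30/360 = 0.18 mm² or 2.13 × 44/360 = 0.26 mm², against 2.13 × 15/360 = 0.09 mm². The SAP already accepts this in the EOM arms. The change does not reach make-up images taken at the next scheduled visit (footnote N), because those visits are nominal.

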#### **8.1.5. Early Termination Visit**

A list of all assessments to be performed at the early termination visit can be found on the Visit Schedule. All subjects who end the study early for any reason must complete the early termination visit, however all efforts should be made to have the subject return for as many follow-up visits as possible even if dosing does not occur. All ophthalmic procedures are to be performed on **BOTH EYES**.

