### **9.14. Ocular Imaging**

The following ocular images will be obtained and sent to the reading center as outlined in the visit schedule. A reading center manual along with training materials will be provided to all sites which will provide information on standardized procedures for the collection, storage, and

transmission of all images. Prior to any images being taken at the site, site personnel must be properly trained and certified and test images and systems and software must be certified and validated by the reading center. Only trained and certified site staff delegated the responsibility of image collection should perform this task. Ocular images obtained as part of this study are:

- digital color fundus photographs
- FA
- SD-OCT imaging
- FAF (Heidelberg Spectralis instrument)
- NIR
- Endothelial cell count (specular microscopy): select sites only
- OCT-A: select sites only

If a patient misses a visit during which ocular images should have been taken, the images should be collected at the next scheduled study visit.

In the event that a subject is suspected to have new active CNV in the study eye and/or the fellow eye, an SD-OCT and FFA using the protocol specified procedures should be performed and sent to the reading center to confirm the diagnosis ([Section 7.5.1](#)). In addition, in select sites, OCT-A should also be captured according to the study imaging protocol and sent to the reading center.

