16. APPENDICES

**APPENDIX A: VISIT SCHEDULE—Monthly Group—Screening, Day 1 Through Month 12**

	Screening	Treatment														Early Term A
Visit #	1	2	2A	3	4	5	6	7	8	9	10	11	12	13	14	
Day	-28 to -1	1	7	30	60	90	120	150	180	210	240	270	300	330	360	
Week	0	0	1	4	8	12	16	20	24	28	32	36	40	44	48	
Month	0	0	0	1	2	3	4	5	6	7	8	9	10	11	12	
Window (+ or - days)	2	0	1	8	8	8	8	8	8	8	8	8	8	8	8	
Informed Consent/Assign Screening Number	x															
Demographic Data	x															
Inclusion/Exclusion Criteria B	x	x														
Medical/Surgical/Ocular History C	x															
Blood Draw—Safety Labs D,E,F	x	x			x				x						x	x
Urine Sample Collection D,E,F	x	x			x				x						x	x
Urine Pregnancy Test D,E,F		x		x	x	x	x	x	x	x	x	x	x	x	x	
Blood Draw—PK and Complement Profile (C3, CH50, AH50) D,S		x	x	x					x						x	x
Blood Draw—Genotyping (if applicable) D					x											
Blood Draw—Anti-Pegcetacoplan Ab D		x		x	x				x						x	x
Blood Draw for Clinical Repository (if applicable) D,G					x				x						x	x
Vital Signs H	x	x		x	x	x	x	x	x	x	x	x	x	x	x	x
Physical Examination I	x														x	x
BCVA J	x	x		x	x	x	x	x	x	x	x	x	x	x	x	x
LL-BCVA J		x		x	x	x	x	x	x	x	x	x	x	x	x	x
MNREAD or Radner Reading Charts (select countries) J,K		x							x						x	x
Slitlamp Examination	x	x		x	x	x	x	x	x	x	x	x	x	x	x	x

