6.1. Estimands

The primary scientific research question of this study is to assess the effect of pegcetacoplan compared with that of sham at Month 12 regarding the impact on GA lesion progression under-real-life conditions following the ITT principal.

The primary estimand in the study is defined through the following 5 attributes:

- **Population:** GA subjects defined through inclusion and exclusion criteria in the mITT population.
- **Treatment conditions:** The treatment regimen of interest in this study is PM, PEOM, and Sham.
- **Variable (or endpoint):** Change in total area of GA lesions in the study eye from baseline measured by FAF to Month 12.
- **Strategy for addressing intercurrent events:** See description of intercurrent events below.
- **Population-level summary:** Difference in mean change of GA lesion from baseline to Month 12 between pegcetacoplan and sham groups according to MMRM analysis.

The intercurrent events that will be considered are:

- Treatment discontinuation
- Lost to follow up
- Withdrawal from the study

The intercurrent events will be handled with a treatment policy strategy whereby any measured value will be used as is. Missing data resulting from these intercurrent events will be handled implicitly within the MMRM analysis that assumes missing at random.

The key secondary estimands will be defined and analyzed in the similar fashion as the primary estimand. The primary and key secondary estimands are summarized in [Table 2](#).

Table 2: Estimands of Study

Estimand	Definition	Attributes			
		A: Population	B: Variable (or endpoint)	C: Strategy for addressing intercurrent event	D: Population-level summary
		Main Analyses			
Primary	The effect of pegcetacoplan compared to sham at Month 12 in impact on GA progression	mITT	Change in the total area of GA lesions from baseline measured by FAF to Month 12	
 Treatment policy strategy for subjects who discontinue treatment, are lost to follow-up, or withdraw from the study 	Difference in mean change of GA lesion from baseline at Month 12 between pegcetacoplan and sham groups based on MMRM analysis

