6.3.2. Main Analyses of Key Secondary Efficacy Endpoints

6.3.2.1. Monocular Maximum Reading Speed

Maximum reading speed will be calculated per MNRead or Radner user manuals, with no adjustment for reading inaccuracy. An additional step to cap resulting reading speed values at a maximum of 300 words per minute will be implemented. Values above 300 words per minute exceed values reported in the literature for adults with no vision impairment for MNRead (Calabrese et al. 2016) or Radner (Radner et al. 2002; Radner and Diendorfer 2014) assessments. Maximum reading speed will be calculated as the mean of the three highest nonzero reading speeds (or two, or one value, as available) (Baskaran et al. 2019; Patel et al. 2011), except when all words per minute are calculated as 0: then the maximum reading speed will be calculated as 0.

Monocular maximum reading speed in the study eye will be summarized and analyzed in a similar fashion as the primary efficacy endpoint using MMRM described in Section 6.2.2. The model will include treatment (PM, PEOM, Sham), presence of CNV in the fellow eye (yes or no), and baseline GA lesion area ($< 7.5 \text{ mm}^2$ or $\geq 7.5 \text{ mm}^2$) as fixed effects; baseline monocular maximum reading speed as well as the chart type (MNRead or Radner) as covariates, time (in months) as a factor; the time \times treatment interaction term as well as the baseline monocular maximum reading speed \times time interaction term.

The observed values for the monocular maximum reading speed will be summarized by treatment group and visit for both the study and the fellow eye. Summaries will present the descriptive statistics for baseline, absolute values and change from baseline data.

The mean change from baseline in the monocular maximum reading speed of the study eye \pm the standard error as well as the LS mean of the change from baseline in the monocular maximum reading speed of the study eye \pm the standard error will be plotted over time by treatment group.

In addition, the categorical changes (improvements of ≥ 20 to <40 , ≥ 40 to <60 , ≥ 60 and minimal/no change (-20 to 20), worsening of ≥ 20 to <40 , ≥ 40 to <60 , ≥ 60) for the study eye will be summarized by treatment group and visit.

The shift from baseline in the monocular maximum reading speed for the study eye categories over time will be presented by treatment group for the following categories:

- < 40 wpm
- 40 to < 80 wpm
- 80 to <160 wpm
- ≥ 160 wpm

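### SAP 13.4 windows early termination and off-schedule values by visit rather than by endpoint, so most possible early termination days place reading speed and FRI in a month where neither is planned

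*SAP*

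**What the plan says.** **Mapping rule.** SAP 13.4: "Post-baseline unscheduled visits and early termination visits will be mapped to a scheduled visit". The mapped value "will only be used in the analysis if the nominal scheduled visit result is missing". One pair of tables "presents the analysis visit window mapping for unscheduled and early term visits": Table 5 for the monthly regimen, Table 6 for every other month (EOM). Neither distinguishes endpoints. The only override corrects a mapped visit that falls out of order with neighbouring scheduled visits.

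**Schedule.** Protocol Appendices A to D plan the reading charts, FRI and NEI VFQ-25 at Day 1, Months 6, 12, 18 and 24, and early termination (ET). FAF is planned at even months and ET. Protocol 8.1.5: "All subjects who end the study early for any reason must complete the early termination visit". Footnote A of the schedules times ET at least 30 days after the last dosing visit, or at the scheduled visit where the subject decides to stop. Nothing ties it to the six-monthly assessments.

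**Make-up images.** Protocol 9.14: "If a patient misses a visit during which ocular images should have been taken, the images should be collected at the next scheduled study visit".

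**Models.** SAP 6.3.2.1: "Monocular maximum reading speed in the study eye will be summarized and analyzed in a similar fashion as the primary efficacy endpoint using MMRM", with month as a factor and a month-by-treatment interaction, under the unstructured covariance of 6.2.2. Section 6.3.2.2 does the same for FRI. Neither lists the months that enter. Only NL-BCVA (6.3.2.3) and LL-BCVA (6.4.1) have a time-point rule, for year 2.

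**Estimand.** SAP 6.1: "The intercurrent events will be handled with a treatment policy strategy whereby any measured value will be used as is".

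**The concern.** A subject who withdraws on Day 300 has reading speed and FRI tested at the ET visit, and 13.4 labels them Month 10. One who withdraws on Day 100 has them labelled Month 3. Neither endpoint is planned at those months, so the value has no natural level in the model. A subject who leaves before Day 166 then contributes no usable post-baseline reading or FRI value, despite a completed ET visit.

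FAF has a milder form. In year 1 everyone attends monthly, so the make-up for a missed even-month image is taken at an odd-month scheduled visit. Because 13.4 keeps nominal labels for scheduled visits, it stays at the odd month.

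Withdrawing subjects are those for whom missing at random is least secure. Their last functional measurement is what would make that assumption easier to defend, and reading speed and FRI are formally tested at Month 24.

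**Working it through.** The documents state no figure on this point, so there is none to reproduce.

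**1. Days in windows with a planned reading or FRI assessment (Tables 5 and 6, Days 2 to 720 = 719 days).**

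| Window | Monthly | EOM |
|---|---|---|
| Month 6 | 166–195: 30 | 166–195: 30 |
| Month 12 | 346–375: 30 | 346–375: 30 |
| Month 18 | 526–555: 30 | 511–570: 60 |
| Month 24, to Day 720 | 706–720: 15 | 691–720: 30 |
| Total | 105 | 150 |

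Unplanned, monthly: 719 − 105 = 614; 614/719 = 85%.
Unplanned, EOM: 719 − 150 = 569; 569/719 = 79%.
Table 6 puts Day 690 in both Month 22 and Month 24. It is counted here as Month 22; the alternative changes the EOM count by 1.

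Year 1, both regimens (Days 2 to 375 = 374 days): 374 − 60 = 314; 314/374 = 84%.

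**2. Sensitivity to the day range.** Footnote A makes the first 30 days unlikely for ET. From Day 31 there are 690 days: monthly 690 − 105 = 585 (85%); EOM 690 − 150 = 540 (78%).

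**3. Sensitivity to withdrawal timing.** The documents do not give it. Under uniform, front-loaded and back-loaded linear withdrawal, starting on Day 2 or Day 31 and ending at Day 719 or at the end of the Month 24 visit window (Day 728 monthly, 736 EOM), the unplanned share was 82% to 87% monthly and 70% to 85% EOM. It was a majority in every case.

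**4. FAF, year 1.** Six even-month windows of 30 days = 180; 374 − 180 = 194; 194/374 = 52%. Over the whole study (to Day 728 monthly, 736 EOM) it is about 51% monthly and 26% EOM, because every year-2 EOM window is an even month.

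**5. Does an off-schedule value inform Month 24 if it is kept?** Illustration with arbitrary numbers: one group of 200 simulated subjects, a free mean at each month, a known covariance, and 30 withdrawers who have a Month 6 value and an ET value in the Month 9 window.

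| Handling of the 30 ET values | Month 24 mean | Month 24 mean, ET values lowered by 20 |
|---|---|---|
| Dropped | −23.76 | −23.76 |
| Kept as a Month 9 level | −23.76 | −23.76 |
| Assigned to Month 12 | −23.53 | −25.82 |

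A month populated only by withdrawers has its own mean, which absorbs whatever they scored. With an estimated unstructured covariance, its covariance with later months cannot be estimated either, since no subject has both. Keeping the value therefore gains nothing at Month 24. Assigning it to a planned month moves the Month 24 mean by 25.82 − 23.53 = 2.29 under the same shift. This shows the mechanism; it is not a forecast of bias.

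**The case against.** **The SAP never says these values are deleted.** That is correct. Read literally, no nominal reading result exists at Month 10, so the condition for using the ET value is met. But step 5 shows that a Month 10 level would not help the Month 24 comparison, and the out-of-order override does not move a value to a planned month.

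**Only planned visits are evidently meant.** The tipping-point text in 6.2.3.1 counts six even-month visits to Month 12, and the sample code lists visits explicitly. If so, off-schedule values are dropped, which is the loss described here.

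**Departures from missing at random are already examined.** SAP 6.3.3 repeats the control-based and tipping-point imputations for the key secondary endpoints at 24 months. That stands as partial cover, but those analyses would impute where function was measured.

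**Wide windows have their own bias.** In a progressive disease, entering a Day 631 value as Month 24 credits a withdrawer with about three months' less decline, and unequal withdrawal between arms could carry that into the contrast. This stands, and is why the fix needs bounds and a sensitivity analysis.

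**Stronger readings that a reader might infer, and that the documents do not support:**
- That the SAP no longer estimates its treatment-policy estimand. Section 6.1 says how intercurrent events are handled; it is not a windowing rule. A Day 300 value is not a Month 24 outcome, so omitting it loses auxiliary information without changing the target.
- That all three key secondary endpoints suffer alike. NL-BCVA is measured monthly in year 1 in both regimens; it is affected only at odd-month ET visits in year 2 of the monthly regimen.
- That extra sparse levels will force the autoregressive fallback of 6.2.2. That is conjecture.
- That a particular number of subjects is lost. No dropout rate is given, reading is tested only in select countries, and the synopsis and Protocol 11.8 describe ET attendance as encouraged or offered, where 8.1.5 requires it.

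**Conclusion.** The point holds as a weakness in a stated rule. One set of visit windows serves endpoints with different schedules. As a result, about 85% (monthly) and 79% (EOM) of possible ET days place reading speed, critical print size, FRI and VFQ-25 at a month with no planned assessment, and 52% of year-1 days do so for FAF. The exact shares rest on counting every day equally; other withdrawal timings gave 70% to 87% for the six-monthly endpoints.

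The consequence is lost information on withdrawing subjects and a heavier reliance on missing at random for the Month 24 reading and FRI comparisons. Planned values obtained before withdrawal stay in the model, and ET visits inside the Month 6, 12, 18 or 24 windows are placed properly. No bias in the treatment contrast has been shown. The change should be made before the final analysis, because otherwise the choice falls to programming after analysis personnel have been unmasked at Month 12 (SAP 3.5).

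**What to change.** In SAP 13.4, add endpoint-specific windows, identical in all arms and used only when the planned value is missing:

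- **FAF:** assign ET, unscheduled and make-up values to the nearest even month, within about 1 month, with a stated tie rule for images midway between two even months. Reconcile this with SAP 3.6, whose Day 375 cutoff for subjects without a Month 12 visit would exclude a make-up image taken at Month 13.
- **Reading speed, critical print size, FRI, VFQ-25:** use bounded windows around Months 6, 12, 18 and 24, for example Days 91–270, 271–450, 451–630 and 631 to end of study. Leave earlier values unplaced; without a lower bound, a Day 31 value would move 180 − 31 = 149 days, about 5 months.
- **Models:** list the planned months in each MMRM.

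The example windows place Days 91 to 728, or 638 of 727 days (88%), against 113 of 727 (16%) now in the monthly regimen. These count placement rather than use: a Day 250 value falls to Month 6 and is not needed if Month 6 was attended.

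**Cost:** one table and programming, with no new data. A mapped six-monthly value can lie up to about 3 months from its target (270 − 180 = 90 days). So report the number of mapped records by arm, and repeat the Month 24 reading and FRI analyses without them as a sensitivity analysis.
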